- 4.) Should study staff receive no reply within 2 weeks, staff members will call the patient on the phone to assess interest in the study and to describe the study over the phone. If the patient remains interested, staff will confirm eligibility and assess for exclusion criteria. If the patient remains interested and appears eligible, study staff will set up an appointment time to go through the consent procedures and conduct the initial study visit. We will then mail or e-mail participants a consent form to look over ahead of time, so that they may prepare questions for the first visit. Note: If a participant prefers to perform all study visits by phone, a consent form will be mailed to the participant. This will be reviewed over the phone, and if the patient remains interested, he or she will sign the consent form and mail it back to study staff at MGH. Once the signed consent form is received, study staff will mail study materials to the participant, and the participant will be called for the first study visit.

For potentially eligible patients who are enrolled in the MGH Research Options Direct to You (RODY) Program, we will directly contact them via phone to inform them about the project. RODY identifies patients who are willing to be contacted directly about research studies. Patients who have agreed to be contacted directly are identifiable through the RPDR search; each patient's RODY status is available in the demographics table included in the RPDR output.

Future Studies. For participants approached either inpatient or outpatient, we will inquire at the end of the screen about whether they are interested in being contacted for future studies. This will allow us to create a database for contacting patients regarding any research studies we conduct in the future.

IV. PARTICIPANT ENROLLMENT

A. Methods of Enrollment

We will enroll participants through the recruitment procedures, described above, and the informed consent procedures, described below.

B. Procedures for obtaining informed consent

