Finally, once a participant signs the consent form, the investigator will perform a focused review of the participant's medical record (including laboratory data) to again confirm that the patient has HF, and will consult with the study cardiologist in the event that there is any need for further clarification. If there is question about the patient's medical prognosis (to assess whether the patient has a condition likely to lead to death within 6 months) the study team will consult with the patient's inpatient or outpatient team and/or the study cardiologist. Participants will be asked to sign a release form at the time of consent to allow study staff to discuss their diagnosis and aforementioned medical variables during the study.

Partners Healthcare has an electronic system that lets the participants' study doctors know if they are admitted to a Partners Hospital, or if they visit a Partners Hospital Emergency Department. We will

use this system to ensure that the study doctors know about any possible problems or side effects participants experience while taking part in the study.

C. Treatment assignment/randomization

There is no randomization procedure required for this trial.

V. STUDY PROCEDURES

A. Study visits/evaluations (See Table 1)

Initial visit (Week 1; in person). The initial visit will occur in an MGH inpatient unit, in the outpatient cardiac clinic, in a designated private office within the CPRP suite (for those contacted via opt-out letter), or over the phone (if a participant prefers to not come to the hospital for an in-person visit). Participants will meet with a member of the study staff (the study “trainer”) and complete self-report questionnaires. These questionnaires assess optimism (Life Orientation Test-Revised; LOT-R),⁵⁵ anxiety/depression (Hospital Anxiety and Depression Scale; HADS),⁵⁶ positive emotions (Positive and Negative Affect Schedule; PANAS),⁶⁵ health-related quality of life (MOS Short Form-12; SF-12),⁵⁷ cardiac symptoms and heart failure-related quality of life (Kansas City Cardiomyopathy Questionnaire; KCCQ),^{58,59} medication adherence (Self-Reported Medication Adherence [adapted from the Heart and Soul Study]; SRMA),⁶⁰ and sodium intake (Scored Sodium Questionnaire; SSQ).⁶¹ Participants will also answer questions about their alcohol (using the AUDIT-C)⁶² and cigarette use. In sum, these scales should take approximately 30 minutes to complete.

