Week 5: Setting a SMART heart-healthy diet goal.

Participants will be encouraged to set a small behavioral goal related to diet and to continue to monitor their sodium intake.

Week 6: Heart-healthy diet resources.

Participants will be asked to identify resources (community, friends/family, low sodium diet recipes/books) for having a low sodium diet and how they can use them to work toward their goals. They will also discuss ways to problem solve around barriers to a heart-healthy diet.

Module 3: Medication adherence

Week 7: Introduction to medication adherence.

The trainer will review with participants the importance of medication adherence, as well as participants' current medication adherence. Participants will be encouraged to monitor their medication adherence over the next week.

Week 8: Setting a SMART medication goal.

Participants will be encouraged to set a goal related to medication adherence and to continue to monitor their medication adherence.

Week 9: Medication resources.

Trainers and participants will discuss different resources (e.g., medication pill boxes, electronic reminders) that can help participants remember to be adherent to their medications. They will also discuss ways to problem solve around barriers to medication adherence.

Week 10: Planning for the future.

Trainers will assist participants with reviewing their accomplishments and benefits gained from health behavior adherence thus far, and help them to create a plan for physical activity, heart-healthy diet, and medication adherence for the near future

At each session, health behavior goals will be reviewed with the participant, and if there are any concerns about the goals, participants will be encouraged to speak with their outpatient treatment team for clarification. Educational information will be based on the *Learning to Live with Heart Failure* guide,⁶³ which is provided to all patients with HF who are admitted to an MGH cardiology unit. Study staff will confer with the study cardiologist if any other questions arise.

Given the results of our prior PP studies, and given that this is a feasibility study (i.e., we want to assess participants' willingness to complete the exercises), we will expect participants to complete at least 5 PP exercises / goal-setting sessions. In other words, if a participant completes at least 5 sessions, missed sessions will not be considered a deviation from the protocol.

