Follow-up phone call (Week 10). At Week 10, a member of the study staff will call participants to repeat the self-report questionnaires that were administered at baseline. These questionnaires assess optimism (LOT-R), positive emotions (PANAS), overall health behavior adherence (MOS SAS), anxiety/depression (HADS), health-related quality of life (SF-12), cardiac symptoms and heart failure-related quality of life (KCCQ), medication adherence (SRMA), and sodium intake (SSQ). Participants will also be asked about alcohol use (AUDIT-C), cigarette smoking, cardiac-related hospital readmissions, and cardiac rehabilitation, and to rate their overall satisfaction with the treatment they received for their cardiac condition over the last 10 weeks on a scale of 0 (not at all satisfied) to 10 (completely satisfied). Finally, patients will be asked about their experience in the study, including any aspects of the intervention or study procedures that could be improved, during follow-up assessment. In sum, these scales should take approximately 30-40 minutes to complete. If participants would rather complete the follow-up questionnaires in written form rather than over the phone, we will send them a paper packet at the time of the follow-up.

Training. [name] (PI) and [name] (LICSW) have substantial experience in explaining and delivering PP exercises from their studies in cardiac and psychiatric patients. The PP exercises for this trial have been identified via published literature,^{33,65-68} or directly from researchers, and modified appropriately for this population. Additional text outlining the rationale and instructions for each exercise are located in the written packets for each exercise that are provided to participants. [name] and [name] will engage in several training exercises prior to study initiation. Together, they will review the treatment manual and our team's prior training manuals related to these exercises. They then will complete all exercises together to gain experience performing and reviewing each exercise.

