Informed consent process. With regard to the consent process, we will approach/recruit participants in the hospital only after patients' treatment team members (who would not be associated with the consent process in any way) ask patients if they are interested in hearing more about an optional study. In the outpatient setting, we will only contact those participants who express interest in the study or do not opt out after receiving an opt-out letter. If an investigator is clinically caring for a potential participant, an alternate, trained study staff member will approach the patient and complete the informed consent process and all study procedures for that participant. When discussing the study, we will emphasize the study's optional nature and participants' ability to opt out/un-enroll at any time, for any reason.

Medical & psychiatric emergencies. If patients report acute medical symptoms, they will be directed to emergency medical care, and their primary medical physicians may be contacted as needed. If study staff have questions regarding medical symptoms and their urgency, [name] (co-investigator and cardiologist) and the PI will be available to consult (and call patient) as needed. This study utilizes a questionnaire that assesses depressive symptoms (HADS), and thus, participants might disclose information about suicidal thinking or behavior. Due to this possibility, the follow-up call will be performed at a time when a psychiatrist study investigator is available to intervene as needed. If participants report suicidal ideation, study staff will complete specific suicide risk assessment questions to assess immediate risk of self-harm, and the psychiatrist will immediately assess the situation/patient if there is either an acutely elevated risk of self-harm or if additional information is needed to clarify risk. If the patient is at imminent risk, the study psychiatrist will take all needed steps to ensure emergent evaluation, which may include ensuring evaluation in the nearest emergency room. Participants will be informed of all of these measures to ensure confidentiality—and the limits of confidentiality, such as arranging for emergent medical or psychiatric care if safety is at imminent risk—as part of the informed consent process. However given that this is a medical rather than a psychiatric population we anticipate the rate of suicidality in this population will be low.

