We will ask participants to report adverse events related to study participation they may have experienced at any time throughout the study. Any adverse events will be reported to the PI and to the IRB according to Partners HRC guidelines.

E. Radiation risks

There will be no radiation exposure in this study.

VI. POTENTIAL BENEFITS

A. Potential Benefits to Participants

It is possible that participants will not receive benefit from participation. Patients will undergo a series of exercises that are designed to increase optimism, improve well-being, and potentially improve cardiac health behaviors. Analyses of PP studies have been that these interventions are associated with improved psychological well-being and decreased depressive symptoms, and optimism

is associated with superior medical outcomes. Therefore, participating individuals may benefit by having improvements in these important and clinically relevant outcomes. Overall, contact with study trainers and the systematic follow-up assessments may also provide support and social connection for participants at a time of recent medical crisis. This may be an improvement over no such contact or systematic evaluation, as is current standard practice.

Patients will be given the opportunity to identify positive emotions and consider ways to enhance their own positive emotions. Description of the PP exercises may enlighten them as to potential means of improving their own emotional states. Furthermore, they will have the opportunity to consider possible barriers to adherence to health-related behaviors.

B. Potential Benefits to Society

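### The admission alert covers only Partners hospitals, and no scheduled all-cause question on hospital or emergency care elsewhere backs it up

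*Combined protocol and SAP*

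**What the plan says.** The combined protocol and SAP gives four routes by which the study team could learn of a hospital stay or emergency visit.

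- **Electronic alert (section IV.B, end).** The system lets study doctors "know if they are admitted to a Partners Hospital, or if they visit a Partners Hospital Emergency Department". The team will "use this system to ensure that the study doctors know about any possible problems or side effects participants experience".
- **Week 10 call (section V.A, Follow-up phone call).** "Participants will also be asked about alcohol use (AUDIT-C), cigarette smoking, cardiac-related hospital readmissions, and cardiac rehabilitation". This is the only scheduled question on hospital care.
- **Request for adverse events (section VII.D, end of Medical & psychiatric emergencies).** "We will ask participants to report adverse events related to study participation they may have experienced at any time throughout the study". No timing, form or person is named.
- **Weekly trainer calls (section V.A, Weekly phone sessions and Program Content).** Each call's content is listed item by item for the positive psychology and goal-setting parts. No item concerns health events, admissions or adverse events. Table 1 has no adverse event row and places chart review before enrolment and at baseline only.

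Events that become known are then well provided for. Section VIII.B describes ongoing monitoring, weekly meetings and a data safety monitoring board that meets every four months. Section VIII.D has the principal investigator decide, for serious and nonserious events alike, whether the event may be related to the research.

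**The concern.** The purpose given to the alert is wider than its coverage. It is said to make any possible problem known, yet it cannot see a hospital outside one system. The other routes are each limited in a different way: by diagnosis and timing (week 10), by the participant's own view of relatedness (the adverse event request), or by whether the participant happens to mention it (the weekly calls).

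Hospital stays and emergency visits are among the most objective harm signals in this population. Section I.A itself describes heart failure as involving repeated hospitalisation, so such events are to be expected. The monitoring board and the decision to continue, change or stop the study (section VIII.B) can use only events that reach the team. In a cohort this small, one unrecorded admission is a visible share of the safety data.

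**Working it through.** No power, alpha or event-rate figure is involved, and the plan states no number to reproduce. The check sets each type of event against each route as written.

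| Event | Alert (IV.B) | Week 10 question (V.A) | Adverse event request (VII.D) | Weekly call as listed (V.A) |
|---|---|---|---|---|
| Cardiac admission, Partners | Yes | Yes | If participant thinks it study-related | If volunteered |
| Cardiac admission, elsewhere | No | Yes, at week 10 | If participant thinks it study-related | If volunteered |
| Non-cardiac admission, Partners | Yes | No | If participant thinks it study-related | If volunteered |
| Non-cardiac admission, elsewhere | No | No | If participant thinks it study-related | If volunteered |
| Emergency visit without admission, Partners | Yes | No | If participant thinks it study-related | If volunteered |
| Emergency visit without admission, elsewhere | No | No | If participant thinks it study-related | If volunteered |

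**Which events can be missed.** For a non-cardiac admission elsewhere, and for any emergency visit elsewhere, both fixed routes read No. What remains depends on the participant judging the event study-related or raising it unprompted.

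**The relatedness conflict.** Section VII.D has the participant filter on relatedness before reporting, while section VIII.D reserves that judgement for the principal investigator. Take a participant admitted elsewhere after a fall, in a programme that sets physical activity goals (section V.A, Goal-setting). If that person thinks the fall had nothing to do with the study, the event need not be reported and the investigator never assesses it. Sections VIII.B to VIII.D govern review of known events; they do not find new ones.

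**Delay for a cardiac admission elsewhere.** The first visit is in week 1 and the question is asked in week 10, so the longest lag is 10 − 1 = 9 weeks. If the event is mentioned on the next weekly call, the lag falls to about 1 week. The 9 weeks is therefore an upper bound.

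**Scale of one event.** Section VI.D plans 11 participants, with a maximum of 15. One participant is 1/15 = 6.7% to 1/11 = 9.1% of the cohort.

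**Number missed.** This would need an admission rate, the share of care outside Partners, the share that is non-cardiac, and the chance of detection through the adverse event request or the weekly calls. The documents give none of these, so no estimate is offered.

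**The case against.** The strongest reply is that the plan has more safety routes than the alert and the week 10 question. The section VII.D request is not limited to cardiac events, to Partners sites or to week 10. Participants are due to speak with a trainer every week, and adverse events are discussed weekly and sooner if needed. This stands, and it rules out saying that the week 10 question is the only backup or that outside events will be missed. They can be missed. It does not close the gap, because the request is restricted to study-related events, has no schedule and does not appear in the listed call content. Table 1's silence alone is weaker evidence, since that table also omits the week 10 readmission question.

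A reader might be tempted by several stronger readings. The documents do not support them.

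- **That phone-only participation shows that care is received elsewhere.** Section III.B says "If a participant prefers to perform all study visits by phone, a consent form will be mailed to the participant". That is a preference about study visits and says nothing about where a person is hospitalised. Participants are recruited from Massachusetts General Hospital inpatient units and its Heart Center.
- **That emergency referrals go unseen.** Section VII.D mentions steps "which may include ensuring evaluation in the nearest emergency room", but the study psychiatrist takes those steps, so the team would know of the visit.
- **That missed calls disappear after session 5.** Section V.A says "if a participant completes at least 5 sessions, missed sessions will not be considered a deviation from the protocol". The weekly meetings in section VIII.B also cover feasibility information, and session completion is the feasibility measure, so missed calls can be seen there.
- **That outpatients would answer no to a question about readmission.** Section V.A lists topics, not the wording put to participants.
- **That the primary result is biased.** The feasibility criterion counts completed sessions. The reason for a missed session affects interpretation, not the count.
- **That a percentage missed can be given.** Any such figure would rest wholly on assumed inputs and would have to ignore the section VII.D request.

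**Conclusion.** The concern holds in a limited form. Section IV.B claims more for the alert than a Partners-only system can deliver, and the other routes reduce the gap without closing it. Followed exactly, the plan can miss a non-cardiac admission or any emergency visit outside Partners that the participant regards as unrelated. It can also learn of a cardiac admission elsewhere up to about 9 weeks late if no weekly call brings it out.

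This rests on the call content and schedule as written; an unpublished call script with a health-event question would narrow it. It also assumes that some participants receive some acute care outside Partners, which is plausible but not quantified in the documents. The primary completion count is unaffected. The change should be made because it is a specific safety gain on calls already planned.

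**What to change.** 1. **Section V.A, Follow-up phone call.** Replace "cardiac-related hospital readmissions" with any hospital stay or emergency visit at any hospital since the last contact, with the reason. The study team classifies each as cardiac or non-cardiac.
2. **Section V.A, Program Content, and Table 1.** Ask the same brief question at each weekly call and add a row to the table.
3. **Section VII.D.** Remove the study-related restriction from the request, so that participants report all adverse events and the principal investigator judges relatedness as section VIII.D provides.
4. **Section IV.B.** State that the alert covers Partners sites only, and name the weekly question as the route for care elsewhere.

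Optionally, record the reason for each missed call. This would help in interpreting feasibility, for instance by separating a hospital stay from lost interest, and leaves the completion criterion as it is. A weekly question cannot reach someone who has stopped answering; for that person the widened week 10 question is the fallback, if the call is answered.

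The cost is protocol and call-script wording, one field on the weekly form, a little more call time, and some self-reported events without records behind them. The investigator will also review more events that prove unrelated, a small load with at most 15 participants.

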After completion of the questionnaires, participants will be provided with a treatment manual, with weekly PP exercises and information to teach participants about the importance of health behaviors and set goals to improve these behaviors. They also will receive a copy of *Learning to Live with Heart Failure*,⁶³ a practical guide which is provided by MGH to all HF patients admitted to a cardiology unit at MGH.

The trainer then will introduce the participant to the PP and goal-setting portions of the intervention. For the PP portion, participants will be assigned the first exercise (gratitude for positive events) and will be instructed to perform the exercise within the next week. Prior to completing the exercise, participants will be asked to rate their current level of happiness and optimism, using a 10-point Likert scale. Immediately after completing the exercise, participants will rate the ease of exercise completion, overall utility of the exercise, and their current levels of happiness and optimism, all using 10-point Likert scales. For the first goal-setting session, the trainer will discuss the importance of physical activity in HF. Participants will be given a pedometer, which participants will use to monitor the number of steps they take daily over the following week. The trainer will instruct them in its use and set a goal for monitoring their baseline physical activity over the next week. This pedometer will not be used as an outcome measure but simply will be a tool that participants can use to monitor their activity. We anticipate that this portion of the visit will take approximately 20 minutes.

After assigning the first week’s PP and goal-setting exercises, participants will receive an Actigraph GT3X+ accelerometer, and its use will be demonstrated by the trainer. We will measure activity at baseline (for 7 days) and in the 7 days following the 10-week assessment (we will send participants the ActiGraph in the mail at the appropriate time). In contrast to the pedometer, which is used for participants to monitor their activity, the ActiGraph accelerometer provides no information to

participants about their physical activity and will only be used by the study team to measure physical activity as an outcome.

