ActiGraph accelerometers are validated as measures of physical activity and have been used in numerous studies of physical activity in patients with medical illness.⁶⁴ The accelerometer is a small 1.5" square device that can be worn on an elastic band (around the lower waist) or clipped onto a belt. It tracks the number of steps taken. After explaining how to use the accelerometer, the study trainer will schedule an appointment to call the participant in 1 week to review the first exercise. In total this initial visit will take approximately 50-60 minutes.

Weekly phone sessions (Weeks 1-10). All participants will be asked to complete 9 weekly PP exercises and will be asked to speak with a study trainer weekly. In addition, in Week 10, there will be a wrap-up phone call that focuses on the progress the participant has made in the program and makes a plan for continuing to use PP skills and engage in healthy activities in the future. Weekly phone sessions will last approximately 30 minutes. These calls will be recorded so that a percentage (10%) of these recordings can be reviewed to ensure that the PP and goal-setting portions of the intervention are being delivered as described in the protocol and trainer manual.

Program Content. All phone sessions will include (a) a review of the week's PP exercise (including the participant's ratings of pre- and post-exercise happiness, ease and helpfulness of the exercise, and optimism related to the future), (b) a discussion of the rationale of the next week's PP exercise through a guided review of the PP manual, and (c) assignment of the next week's PP exercise. Additionally for the goal-setting portion, participants will (a) review their goals and behaviors from the prior week, (b) discuss techniques for improving health behavior adherence (e.g., monitoring physical activity, reading nutrition labels), and (c) set goals for the next week. The exercises and content for both PP and MI will be assigned in the same order for all participants receiving them. During the calls, the trainer and participant will also review the next section of the treatment manual and prepare for the upcoming week's exercise.

Positive Psychology Exercises. The PP exercises used in this study were selected based on their superior performance in our pre-pilot research and others' work. They will be grouped into three-week modules focusing on a different psychological state:

Module 1: Gratitude-based activities

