Goal-setting. The goal-setting portion of the program aims to provide patients with knowledge about important HF-related health behaviors and assist them with setting goals to become more adherent to these health behaviors. This intervention will focus on three distinct health behaviors: physical activity, low-sodium diet, and medication adherence. These also will be divided into three-session modules, which will be completed in parallel to the PP exercises.

Each session follows the same structure. Study trainers will: (a) ask participants about their health goals, (b) provide education about a health behavior and/or refer them to their treatment team if clarification is needed, and (c) set a health behavior goal for the next week. Health behavior goals will be individualized to the participant, and participants will be encouraged to speak with their treatment team if they have any questions about appropriate goals for diet or physical activity. While all sessions

will involve tracking participants' progress towards their health behavior goals, the educational components will vary from week to week:

Module 1: Physical activity

Week 1 (in-person visit): Introduction to increasing physical activity.

The trainer will review with participants the potential health benefits of physical activity, as well as participants' current physical activity. Participants will receive a pedometer and set a goal of monitoring their physical activity (through steps measured by the pedometer) over the next week.

Week 2: Setting a SMART physical activity goal.

Participants will learn about setting goals that are SMART (specific, measurable, attainable, relevant, and time-based) and will be encouraged to set a small behavioral goal related to physical activity.

Week 3: Physical activity resources.

Participants will be asked to identify resources (community, friends/family, equipment) for engaging in physical activity and how they can use them to work toward their goals. They will also discuss ways to problem solve around barriers to physical activity.

Module 2: Heart-healthy diet

Week 4: Introduction to a heart-healthy diet.

The trainer will review with participants the potential health benefits of a low sodium diet, as well as participants' current dietary habits. Participants will be encouraged to keep track of their salt intake over the next week and contact their physician if they are unsure how much sodium they should be consuming daily.

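### The seven-day ActiGraph baseline is worn during intervention Week 1, and the re-wear rule can carry it past the Week 2 activity goal, so the exploratory step change may not start from usual activity

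*Combined protocol and SAP*

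**What the plan says.** Section V.A (Initial visit) sets the order. Questionnaires come first, then the treatment manual, the first PP exercise and a talk on why activity matters in heart failure. Next comes the pedometer: "Participants will be given a pedometer, which participants will use to monitor the number of steps they take daily over the following week". The trainer is also to "set a goal for monitoring their baseline physical activity over the next week". The outcome device comes last: after the first week's "PP and goal-setting exercises, participants will receive an Actigraph GT3X+ accelerometer, and its use will be demonstrated by the trainer". Section V.E (Baseline Data) starts wear after the initial visit (the noun is missing from that sentence, but no other reading fits).

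The measurement windows are given as: "We will measure activity at baseline (for 7 days) and in the 7 days following the 10-week assessment". The outcome device is silent; "the ActiGraph accelerometer provides no information to" participants about their own activity, and section V.E (a) has its notifications turned off.

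The Goal-setting part of section V.A places the same content in the intervention. Module 1, Week 1 reads "Participants will receive a pedometer and set a goal of monitoring their physical activity (through steps measured by the pedometer) over the next week". The next entry is "Week 2: Setting a SMART physical activity goal".

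Section V.E (a) defines a valid day (480 minutes of wear) and a complete record (5 valid days), counts steps over the final seven days of wear, and asks anyone short of 5 valid days to wear the device again until they have them. It gives no latest date. Sections VI.A/B and VI.C compare baseline with 10 weeks by paired t test, under the Exploratory Aim of section II.

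**The concern.** The trial has one arm, so the baseline week is the only comparator for ActiGraph steps. Sections III.A and V.E call steps the leading health behavior outcome. A baseline is useful here only if it reflects activity before the program acts on it. The questionnaires meet that condition because they are completed before any content; the step count does not.

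The plan keeps the outcome device silent, yet gives participants a second device that shows their steps on the same days. In describing the phone sessions, the protocol treats self-monitoring as a lever: trainers are to "discuss techniques for improving health behavior adherence (e.g., monitoring physical activity, reading nutrition labels".

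If Week 1 content moves steps, the contrast omits part of the effect, and no later analysis can recover the missing usual-activity level. Open-ended re-wear could extend the problem into weeks that carry an explicit activity goal.

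**Working it through.** The protocol gives no step count, SD, effect size or power for this comparison, so there is no figure to reproduce. The check is of sequence, followed by simple algebra.

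**1. Which days are baseline.** Content is delivered at the initial visit (V.A), wear starts after it (V.E), and wear lasts seven days (V.A). No section describes earlier wear or a run-in. The baseline days are therefore the days of Module 1, Week 1, including the period set for the first PP exercise.

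**2. What re-wear does.** A participant with v valid days, v = 0 to 4, is asked to wear the device again. If valid days accumulate, at least 5 − v more are needed: from 5 − 4 = 1 to 5 − 0 = 5. If k days are re-worn (k up to 7), the final seven days of wear contain k re-worn days and 7 − k original days. So between 1 and 7 of the seven scored days could come from re-wear.

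Section V.E does not date the re-wear. Section VII.C has the device mailed back after 7 days, section VII.D has its data read only on a site computer, and section V.A schedules the first call at one week. Together these suggest that a shortfall would usually come to light at or after the Week 2 session, when the SMART goal is due. That is an inference, so the claim is only that baseline days could fall there.

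**3. Direction of the error.** Let U be usual activity, F follow-up activity, w the rise in scored baseline steps due to program content, and h the reduction due to days in hospital or just after discharge. Then

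- measured baseline = U + w − h
- measured change = F − (U + w − h) = (F − U) − w + h

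The error is h − w. With h = 0 and w > 0 the change is understated; with w = 0 and h > 0 it is overstated. Neither term is given. Section V.A allows the initial visit on an inpatient unit, so h need not be zero. Section V.E (c) asks hospitalized participants about sodium intake before admission, but nothing comparable is provided for steps.

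**4. Illustration, on assumed inputs only.** Take h = 0, let f be the share of the eventual gain already present at baseline, and d the true gain in SDs of change. The visible gain is (1 − f)d. For the planned two-sided paired t test at 0.05 with 10 completers (9 df, noncentrality (1 − f)d√10), power is:

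| d | f = 0 | f = 0.25 | f = 0.50 |
|---|---|---|---|
| 0.5 | 0.293 | 0.186 | 0.109 |
| 0.8 | 0.616 | 0.396 | 0.205 |
| 1.0 | 0.803 | 0.562 | 0.293 |

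At f = 0 nothing is lost. The table shows how sensitive the contrast would be if f were material; it is not an estimate of f. Whatever the baseline, the 95% interval half-width at n = 10 is t(0.975, 9)/√10 = 2.262/3.162 = 0.72 SD of change.

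**5. Which decisions use this number.** Feasibility (VI.A/B, Aim 1) rests on sessions completed and on adequate accelerometer data at 10 weeks. The next-step rule rests on feasibility, fit with the qualitative work, and some effect on optimism or positive affect. Neither uses the step change.

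**The case against.** The strongest reply is that Week 1 is light by design. Its activity goal is monitoring only, the protocol itself calls this baseline activity, the first goal to change behavior comes in Week 2, and the ActiGraph shows the participant nothing. The sentence naming monitoring as an improvement technique concerns the phone sessions, not the initial visit. No section shows that Week 1 content changes steps. The contrast is exploratory and expressly unpowered, and the device is used here largely to test feasibility. All of this stands and limits the severity. None of it makes the week pre-intervention.

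It is also fair that a clean baseline would not make the change attributable to the program. There is no control arm, and section III.A selects people with low self-reported adherence, exercise included, so regression to the mean could inflate the gain.

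Three stronger readings are tempting and should be resisted.

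- A reader might infer from the 80% accelerometer criterion that about a fifth of participants will need baseline re-wear. That criterion is completeness at 10 weeks among all enrolled, after any re-wear; it is not a first-wear rate at baseline. No count follows from it.
- A reader might compare an assumed shift with the 0.72 SD half-width and call the bias smaller than the noise. Any such shift reflects only the chosen d and f.
- A reader might apply the show-promise sentence in section VI.A/B to steps. It is worded for medical and functional outcomes, and the heading above it lists health behaviors separately.

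Finally, splitting the visit has a real cost in a study this small. That is why a wording-only alternative is given below.

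**Conclusion.** The concern holds as a point of sequence: the ActiGraph baseline is intervention Week 1, and the scoring and re-wear rules allow some of it to fall later, after the first activity goal. On the sequence the text is clear. On the consequence it is not. Understatement of the step change is conditional on Week 1 or later content raising steps; its size cannot be derived or bounded from the documents, and inpatient days could offset or reverse it. A reader might conclude that the trial's step gain will be too small, or that its go-forward decision is compromised. The documents support neither. This is an inexpensive improvement to an exploratory measure, worth making because the trial exists to refine methods before a larger pilot.

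**What to change.** **Preferred.** Give or mail the ActiGraph at consent or with the baseline questionnaires, and complete the seven-day wear before the manual, activity education, pedometer and first PP exercise. For participants seen by phone, section III.B already mails materials before the first visit; send the ActiGraph first and the rest later. Define baseline steps as the mean over valid days before the Week 1 content. Report later wear separately, show the result with and without participants who have fewer than 5 valid pre-content days, and flag inpatient wear days, which reordering alone does not address. Hold the first session once the seven days have passed rather than waiting for a data download.

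*Cost:* protocol wording, one added contact or mailing per participant, about a week between consent and the first session, and a small added dropout risk in a study capped at 15 enrolled for 10 completers. No new staff or equipment is needed; the device is already mailed for follow-up.

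**Minimum, if the visit order stays.** For baseline, replace the final-seven-days rule with valid days worn before the Week 2 session. Do not count later re-wear as baseline, flag inpatient wear days, and report the contrast as intervention Week 1 versus post-Week 10 rather than as change from usual activity.

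*Cost:* wording only, though some participants may then lack a complete baseline record.
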